9.1.2.2. Concomitant Immunogenicity Hypotheses

9.1.2.2.1. Noninferiority for Percentage of Participants With Prespecified Antibody Level to Each Concomitant Vaccine Antigen at 1 Month After Dose 3 (Primary Concomitant Immunogenicity Objectives)

Hypothesis testing to assess noninferiority of the 20vPnC group to the 13vPnC group for percentage of participants with prespecified antibody level to each concomitant vaccine antigen will be performed similarly to that for the percentage of participants with predefined serotype-specific IgG concentrations, as described in [Section 9.1.2.1.1](#), with π_{20vPnC} and π_{13vPnC} being the percentages of participants with prespecified antibody levels to diphtheria toxoid, tetanus toxoid, pertussis antigens (PT, FHA, PRN), HBsAg, poliovirus strains, or Hib at 1 month after Dose 3 from the 20vPnC and 13vPnC groups, respectively. The following are the prespecified antibody thresholds for the concomitant vaccine antigens:

Antigen	Prespecified Level
Diphtheria	≥ 0.1 IU/mL
Tetanus	≥ 0.1 IU/mL
Acellular pertussis (PT, FHA, PRN)	\geq the observed antipertussis antibody concentration achieved by 95% of 13vPnC recipients

Antigen	Prespecified Level
Hepatitis B	≥ 10 mIU/mL
Poliomyelitis (types 1, 2, and 3)	$\geq 1:8$
Hib	≥ 0.15 $\mu\text{g/mL}$ anti-PRP Alternative: ≥ 1.0 $\mu\text{g/mL}$ anti-PRP

The null hypothesis will be rejected and noninferiority will be declared for a concomitant vaccine antigen if the lower bound of the 2-sided 95% CI for the difference (20vPnC – 13vPnC) in percentages is greater than –10% (10% noninferiority margin) for that concomitant vaccine antigen.

9.1.2.2.2. Noninferiority for GMCs of Antibody Levels to Concomitant Vaccine Antigen at 1 Month After Dose 4 (Secondary Concomitant Immunogenicity Objectives)

Hypothesis testing to assess noninferiority of the 20vPnC group to the 13vPnC group for GMCs of antibody levels to each concomitant vaccine antigen 1 month after Dose 4 will be performed similarly to that for the pneumococcal serotype-specific IgG concentration, as described in [Section 9.1.2.1.2](#), with $\ln(\mu_{20vPnC})$ and $\ln(\mu_{13vPnC})$ being the natural log of the GMCs for antibody levels to measles, mumps, rubella, and varicella viruses at 1 month after Dose 4 from the 20vPnC and 13vPnC groups, respectively.

The null hypothesis will be rejected and noninferiority will be declared for a concomitant vaccine antigen if the lower bound of the 2-sided 95% CI for GMR of the 20vPnC group to the 13vPnC group is greater than 0.5 (2-fold noninferiority margin) for that concomitant vaccine antigen.

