8.1. Efficacy Assessments

8.1.1. Immunogenicity Assessments

Blood samples (approximately 5mL per sample) will be collected from all participants at Visit 4 (1 month after Dose 3), Visit 5 (prior to administration of Dose 4), and Visit 6 (1 month after Dose 4). These are the immunogenicity time points.

Pneumococcal Responses

IgG Responses to the 20 Serotypes Contained in 20vPnC

IgG antibody concentrations for serotypes present in 20vPnC (1, 3, 4, 5, 6A, 6B, 7F, 8, 9V, 10A, 11A, 12F, 14, 15B, 18C, 19A, 19F, 22F, 23F, and 33F) will be determined on all sera collected at the 3 immunogenicity time points (Visits 4, 5, and 6). The serotype-specific IgG concentrations will be measured by Pfizer's multiplex Luminex immunoassay.

OPA Responses to the 20 Serotypes Contained in 20vPnC

OPA titers for serotypes present in 20vPnC (1, 3, 4, 5, 6A, 6B, 7F, 8, 9V, 10A, 11A, 12F, 14, 15B, 18C, 19A, 19F, 22F, 23F, and 33F) will be determined in randomly selected subsets of sera for the immunogenicity time points (Visits 4, 5, and 6). These subsets will be randomly selected, by an unblinded third party, to assure that each subset has equal representation of both vaccine groups. Further details will be described in the clinical specimen assessment plan (CSAP).

CCI [REDACTED]

Concomitant Vaccine Antigens

Responses to the following concomitant vaccine antigens will be assessed. The randomly selected serum subsets to be assayed will be based on minimum sample sizes needed to demonstrate the objectives of the study balanced with the serum volume required and available for testing.

Diphtheria toxoid: Concentration of antibody (in international units [IU]) to diphtheria toxoid (predefined level ≥ 0.1 IU/mL) will be determined on subsets of sera collected at the immunogenicity time point 1 month after Dose 3. CCI [REDACTED]

Tetanus toxoid: Concentration of antibody (in IU) to tetanus toxoid (predefined level ≥ 0.1 IU/mL) will be determined on subsets of sera collected at the immunogenicity time point 1 month after Dose 3. CCI [REDACTED]

Acellular pertussis: Concentration of IgG antibodies to pertussis antigens PT, FHA, and PRN (predefined level \geq the observed antipertussis antibody concentration achieved by 95% of 13vPnC recipients) will be determined on subsets of sera collected at the immunogenicity time point 1 month after Dose 3. CCI [REDACTED]

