9.1.3. Multiplicity Considerations

Pneumococcal Immunogenicity Evaluation

For the primary pneumococcal immunogenicity objectives comparing percentages of participants with predefined serotype-specific IgG concentration levels 1 month after Dose 3, noninferiority will be assessed by the hypothesis test as described in [Section 9.1.2.1.1](#) at an alpha level of 0.05 for each serotype. The primary pneumococcal immunogenicity objectives will be achieved if the noninferiority of 20vPnC to 13vPnC for the percentage of participants with the predefined IgG concentration level at 1 month after Dose 3 is established for all 20 serotypes.

For the primary pneumococcal immunogenicity objectives comparing serotype-specific IgG GMCs 1 month after Dose 4, noninferiority will be assessed by the hypothesis test as described in [Section 9.1.2.1.2](#) at an alpha level of 0.05 for each serotype. The primary pneumococcal immunogenicity objectives will be achieved if the noninferiority of the IgG GMCs from the 20vPnC group compared to the 13vPnC group at 1 month after Dose 4 is established for all 20 serotypes.

The overall primary pneumococcal immunogenicity objectives will be achieved if noninferiority of 20vPnC comparing to 13vPnC based on both the percentage of participants with predefined serotype-specific IgG concentration levels at 1 month after Dose 3 and the serotype-specific IgG GMC at 1 month after Dose 4 is demonstrated for all 20 serotypes. Therefore, the overall type I error rate for the primary immunogenicity assessment of the pneumococcal immune response of 20vPnC is well controlled at the 0.05 level.

Concomitant Immunogenicity Evaluation

For the primary concomitant immunogenicity objective comparing immune responses induced by concomitant vaccine antigens at 1 month after Dose 3 from the 20vPnC group to that from the 13vPnC group, noninferiority is assessed by a hypothesis test (Section 9.1.2.2.1) at an alpha level of 0.05 for each concomitant vaccine antigen. The primary concomitant immunogenicity objective will be met if noninferiority is achieved for all concomitant vaccine antigens, diphtheria toxoid, tetanus toxoid, pertussis antigens (PT, FHA, PRN), HBsAg, poliovirus strains, and Hib. Therefore, the type I error rate for the concomitant immunogenicity assessment is well controlled at the 0.05 level.

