9.2.2. Sample Size Consideration for Concomitant Immunogenicity Objectives

For the primary concomitant immunogenicity objectives, Table 5 presents the minimum evaluable sample size required to demonstrate noninferiority based on the percentage of participants with prespecified antibody levels 1 month after Dose 3 with 10% noninferiority margin for each concomitant vaccine antigen. Evaluable sample sizes needed to achieve 99% power to detect noninferiority for each antigen range from ~36 to ~367 per vaccine group.

Table 5. Sample Size Required With Specified Power to Demonstrate NI Comparing the 20vPnC Group to the 13vPnC Group Based on Percentage of Participants With Prespecified Antibody Levels 1 Month After Dose 3 for Concomitant Antigens, With an NI Margin of 10%

Antigen	Antibody Level Threshold	Assumed Percentage ^a of Participants With Prespecified Threshold Reached		Sample Size per Group With	
		20vPnC	13vPnC	At Least 95% Power	At Least 99% Power
Diphtheria	≥0.1 IU/mL	95	96	177	240
Tetanus	≥0.1 IU/mL	98	98	95	123
PT	≥ Concentration achieved by 95% of 13vPnC group	94	95	201	276
FHA	≥ Concentration achieved by 95% of 13vPnC group	95	95	155	212
PRN	≥ Concentration achieved by 95% of 13vPnC group	93	95	266	367
Hepatitis B	≥10 mIU/mL	100	100	36	36
Polio 1	≥1:8	100	100	36	36
Polio 2	≥1:8	98	99	101	128
Polio 3	≥1:8	100	100	36	36
Hib (PRP)	≥0.15 µg/mL	98	98	95	123

Abbreviations: FHA = filamentous hemagglutinin; Hib = *Haemophilus influenzae* type b;

NI = noninferiority; PRN = pertactin; PRP = polyribosylribitol phosphate; PT = pertussis toxin.

Note: NI criterion for each concomitant antigen: The lower bound of the 2-sided 95% CI for the difference between groups (20vPnC – 13vPnC) in the percentage of participants with specified threshold is above –10%, calculated using the Miettinen and Nurminen method.

- a. Differences between 20vPnC and 13vPnC are assumed to be similar to those observed between 13vPnC and Prevnar in Phase 3 Prevnar 13 Studies 6096A1-004 and 6096A1-3005. Percentages of participants with specified thresholds for 13vPnC are assumed to be the same as observed in the 13vPnC groups in Phase 3 Prevnar 13 Studies 6096A1-004 and 6096A1-3005.

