	
13vPnC group. If the serotype is from the 7 additional serotypes, the IgG GMC in the 20vPnC group will be compared with the lowest IgG GMC among the 13 serotypes from the 13vPnC group, provided that the lowest GMC is not from serotype 3. If the lowest GMC in the 13vPnC group is from serotype 3, the next lowest GMC in the 13vPnC group will be used in the comparison. GMRs and their 2-sided 95% CIs will be derived by calculating differences in means and CIs on the natural log scale of the concentration based on the t-distribution, and then exponentiating the results. The difference in means, on the natural log scale, will be 20vPnC minus 13vPnC. The lower limit of the CI will be used in the hypothesis test for noninferiority of 20vPnC to 13vPnC as detailed in Section 9.1.2.1.2.
 
The analysis will be based on the Dose 4 evaluable immunogenicity population. CCI
 
Participants will be summarized according to the vaccine group to which they were randomized. Missing serology data will not be imputed.

Primary concomitant immunogenicity
	
 • Percentages of participants with prespecified antibody levels to concomitant vaccine antigen 1 month after Dose 3 
For each concomitant vaccine antigen,
 
 a. Antibody levels to diphtheria toxoid, tetanus toxoid, and pertussis antigens (PT, FHA, PRN), b. Antibody levels to HBsAg, c. Antibody levels to poliovirus strains (types 1, 2, and 3), d. Antibody levels to Hib, 
The difference between groups (20vPnC – 13vPnC) and its 2-sided 95% CI for the percentage of participants with prespecified antibody levels 1 month after Dose 3 will be provided. The Miettinen and Nurminen method will be used to derive the CI for the difference in percentages between vaccine groups. The lower limit of the CI will be used in the hypothesis test for assessing the noninferiority of the 20vPnC group to the 13vPnC group as detailed in Section 9.1.2.2.1.
 
The analysis will be based on the Dose 3 evaluable immunogenicity population, restricted to those who also receive the corresponding concomitant vaccines. CCI

Endpoint	Statistical Analysis Methods
	
CCI [REDACTED]
 
Participants will be summarized according to the vaccine group to which they were randomized. Missing serology data will not be imputed.

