### 3.1.3. Primary Concomitant Immunogenicity Endpoints

- Antibody levels to diphtheria toxoid, tetanus toxoid, and pertussis antigens (PT, FHA, PRN) 1 month after Dose 3
- Antibody levels to HBsAg 1 month after Dose 3
- Antibody levels to poliovirus strains (types 1, 2, and 3) 1 month after Dose 3
- Antibody levels to Hib 1 month after Dose 3

Antibody concentrations to each concomitant vaccine will be determined on sera collected 1 month after Dose 3 from a randomly selected subset of participants with sufficient sera volumes. Further details of the subsetting will be described in a memo to the unblinded statistician before any testing proceeds.

To support the primary concomitant immunogenicity estimands, antibody concentrations will be classified based on prespecified antibody thresholds for the concomitant vaccine antigens:

Antigen	Prespecified Level
Diphtheria	$\geq 0.1$ IU/mL
Tetanus	$\geq 0.1$ IU/mL
Acellular pertussis (PT, FHA, PRN)	$\geq$ the observed antipertussis antibody concentration achieved by 95% of 13vPnC recipients
Hepatitis B	$\geq 10$ mIU/mL
Poliomyelitis (types 1, 2, and 3)	$\geq 1:8$
Hib	$\geq 0.15$ $\mu\text{g/mL}$ anti-PRP Alternative: $\geq 1.0$ $\mu\text{g/mL}$ anti-PRP a

a. Secondary concomitant immunogenicity endpoint 1 month after Dose 3.

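### Table 5 sizes PT, FHA and PRN as if the cut-off were known, but the cut-off is read from the 13vPnC sample; with equal SDs, power is about 87-91% and 95-97%, not at least 95% and 99%

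*Protocol*

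**What the plan says.** Protocol 9.1.2.2.1 and SAP 3.1.3 set numerical levels for seven of the ten concomitant antigens. For PT, FHA and PRN the level is "the observed antipertussis antibody concentration achieved by 95% of 13vPnC recipients", and Protocol 8.1.1 uses the same rule. No value, external source or quantile definition is given.

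Noninferiority requires the lower limit of the two-sided 95% CI for the difference to exceed -10%. On the interval, Protocol 9.4.1 states: "The Miettinen and Nurminen method will be used to derive the CI for the difference in percentages between vaccine groups". Protocol 9.1.3 tests "at an alpha level of 0.05 for each concomitant vaccine antigen" and requires all of them to pass for the primary concomitant objective.

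Table 5 (Protocol 9.2.2) labels the threshold in the three pertussis rows "Concentration achieved by 95% of 13vPnC group". It assumes 95% in the 13vPnC group and lists these sizes per group:

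| Antigen | 20vPnC % | n for at least 95% power | n for at least 99% power |
|---|---|---|---|
| FHA | 95 | 155 | 212 |
| PT | 94 | 201 | 276 |
| PRN | 93 | 266 | 367 |

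The text concludes: "Evaluable sample sizes needed to achieve 99% power to detect noninferiority for each antigen range from ~36 to ~367 per vaccine group". Protocol 8.1.1 says the serum subsets to be assayed are "based on minimum sample sizes needed to demonstrate the objectives of the study balanced with the serum volume required and available for testing". SAP 3.1.3 leaves the rest open: "Further details of the subsetting will be described in a memo to the unblinded statistician before any testing proceeds".

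**The concern.** An observed level with no number attached most naturally means the level seen in this trial's 13vPnC infants. The 13vPnC percentage is then about 95% by construction, so it no longer varies as a binomial count. In its place, the error in the cut-off shifts the 20vPnC percentage up or down. Table 5 appears to make no allowance for this.

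The stake is practical. All ten antigens must pass, the Table 5 sizes are the documented basis for how many sera are assayed, and PRN sets the upper figure of 367. If the power behind those sizes is overstated, a subset cut to them carries a larger chance of failing a primary objective than the protocol says.

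**Working it through.** **Inputs.** Percentages and sizes from Table 5; margin -10 percentage points; one-sided 0.025 through the two-sided 95% CI; 1:1 allocation; Miettinen-Nurminen method.

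**Step 1: reproduce Table 5.** Treat the cut-off as known and use the score-test formula for two independent binomials,

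power = Φ{[(p20 - p13 + 0.10) - 1.96·s0] / s1},

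where s0 is the standard error under the restricted estimates (difference fixed at -0.10) and s1 is the ordinary one. The smallest n per group is FHA 155/212, PT 201/276, PRN 266/367, exactly as printed. Diphtheria (177/240), tetanus (95/123) and polio 2 (101/128) also match. An unpooled Wald formula does not: it gives 124/175, 167/236 and 229/324 for FHA, PT and PRN.

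**Step 2: apply the observed cut-off.** Let k = floor(0.05n) + 1 and take the k-th smallest 13vPnC value as the cut-off, so that n - k + 1 infants in 13vPnC reach it. At n = 367, k = 18 + 1 = 19, and 367 - 19 + 1 = 349 reach it (95.1%). The Miettinen-Nurminen criterion then needs at least m = 328 of 367 in 20vPnC.

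- The true 13vPnC proportion below the cut-off is U ~ Beta(k, n - k + 1).
- With normal log concentrations and SD ratio r (20vPnC to 13vPnC), the 20vPnC success probability is p(U) = 1 - Φ{[Φ⁻¹(U) - μ]/r}, with μ = Φ⁻¹(0.05) - r·Φ⁻¹(1 - p20). The Table 5 percentages therefore hold at the true cut-off.
- Power is the average over U of P{Binomial(n, p(U)) ≥ m}.

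| Antigen | n | m | Known cut-off (exact) | Observed, r = 1 | Observed, r = 0.8 to 2 |
|---|---|---|---|---|---|
| FHA | 155 | 142 | 95.7% | 91.3% | 88.3-96.1% |
| FHA | 212 | 192 | 99.3% | 97.0% | 94.8-99.3% |
| PT | 201 | 182 | 95.6% | 89.1% | 85.0-95.8% |
| PT | 276 | 249 | 99.2% | 95.8% | 93.4-98.8% |
| PRN | 266 | 240 | 95.5% | 86.7% | 82.8-93.7% |
| PRN | 367 | 328 | 99.1% | 95.2% | 92.3-98.8% |

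Simulation with 40,000 trials at r = 1 agrees: FHA 91.3/96.9%, PT 89.3/95.7%, PRN 86.7/95.3%.

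**Why power falls.** To first order, the 13vPnC variance term 0.05 × 0.95/n is replaced by (g/f)² × 0.05 × 0.95/n, where g/f is the ratio of the 20vPnC to the 13vPnC density at the cut-off. With equal SDs:

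- FHA: g/f = 1.
- PT: g/f = φ(1.555)/φ(1.645) = 1.155, so the term grows by 1.155² = 1.33.
- PRN: g/f = φ(1.476)/φ(1.645) = 1.302, so the term grows by about 1.69.

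The loss for FHA comes from the skewness and discreteness of the estimated cut-off.

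**Step 3: sensitivity.** The FHA result at r = 1 needs no distributional form, only that both groups share one distribution. Five other log-scale shapes with a pure shift (logistic, t with 5 df, Laplace, Gumbel left and right) give PT 88.4-89.5/95.4-96.0% and PRN 85.3-87.4/94.3-95.7%. Moving the cut-off by one order statistic gives:

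- one lower: FHA 92.3/97.4%, PT 90.3/97.3%, PRN 90.6/95.8%;
- one higher: FHA 86.6/95.2%, PT 84.4/95.2%, PRN 85.2/94.6%.

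The stated power is first met at an SD ratio of about 1.6/1.65 (FHA), 1.75/2.3 (PT) and 2.8/2.25 (PRN).

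**Step 4: effect by subset size (r = 1).** With 367 per group for every antigen, power is FHA 99.8%, PT about 98.7%, PRN 95.2%. If independent, all three pass with probability 0.998 × 0.987 × 0.952 = 0.94, against about 0.99 with a known cut-off. With 500 per group PRN has 98.8%; with 800, each antigen has at least 99.9%.

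**Step 5: the interval.** One-sided non-coverage of the true difference at the realised cut-off was 1.2-2.7% over n = 155 to 800, 20vPnC percentages of 85, 93, 94 and 95%, and r = 0.8 to 2. At a 20vPnC percentage of 85% it was 1.6-2.2%. Nominal is 2.5%.

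**The case against.** The strongest reply is that no loss of power in the trial itself is shown. Table 5 lists minima, not the number of sera to be assayed. The subset size sits in a memo outside these documents, and about 800 evaluable infants per group are expected. The running text cites only the 99% column, and if one subset of 367 were used for everything, only PRN would fall materially short. PT and PRN also need an assumed shape and SD ratio. The 94% joint figure assumes independence, although all three antigens come from one vaccine in the same infants, and positive correlation would raise it. Finally, the Dose 3 follow-up draws were probably largely complete by Amendment 2.

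Most of this limits the consequence, and I accept it. It does not rescue the table. Both columns are stated power figures. Protocol 8.1.1 ties the subsets to these minima and to limited serum from samples of about 5 mL. Meeting the printed power needs a 20vPnC SD roughly 1.6 to 2.8 times that of 13vPnC, which neither document assumes. If the sponsor means a fixed level from an external source, stating its value would settle the point.

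**Conclusion.** The concern holds. The pertussis rows of Table 5 describe a design with a known cut-off, and the protocol specifies an estimated one. Assuming that the cut-off comes from this trial's 13vPnC sera and that log SDs are equal, the chance of missing noninferiority is about 9-13% where the table implies at most 5%, and about 3-5% where it implies at most 1%. PRN is worst affected and stays below its stated power at every SD ratio examined from 0.8 to 2. FHA, and PT at 201, can reach theirs at the upper end of that range.

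That an estimated cut-off was treated as known is firm; the exact power for PT and PRN depends on distributions the documents do not give. The error does not favour a false noninferiority claim: the Miettinen-Nurminen interval is close to nominal, or conservative, for the difference at the realised cut-off.

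**What to change.** 1. In Table 5 and the sentence citing 367, restate power or sizes for PT, FHA and PRN under the observed cut-off, with the distributional assumption. State the quantile rule, for example the highest observed concentration met by at least 95% of 13vPnC infants. Sizes per group from which power stays at or above 95%/99% (log-normal):

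| SD ratio | FHA | PT | PRN |
|---|---|---|---|
| 0.8 | 226/331 | 306/446 | 421/628 |
| 1 | 197/281 | 267/383 | 357/518 |
| 2 | 153/211 | 211/281 | 281/380 |

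   Power moves in small steps with n. At SD ratio 1 the targets are first crossed at FHA 197/278, PT 252/370 and PRN 357/507, and those are the figures if a first crossing is preferred.

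2. Size the assayed subset in the subsetting memo from the restated figures, subject to serum volume. This is the step that can still change the trial's power.

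3. Add one sentence to Protocol 9.1.2.2.1 and SAP 3.1.3 confirming that noninferiority for these antigens is judged at the realised cut-off. This mainly removes ambiguity.

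The cost is table text, a sentence in each document, a line in the memo and a short program. The downside is a less favourable stated power for three antigens, or more sera assayed. Every size above is below 800 per group.

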9.1.3. Multiplicity Considerations

Pneumococcal Immunogenicity Evaluation

For the primary pneumococcal immunogenicity objectives comparing percentages of participants with predefined serotype-specific IgG concentration levels 1 month after Dose 3, noninferiority will be assessed by the hypothesis test as described in [Section 9.1.2.1.1](#) at an alpha level of 0.05 for each serotype. The primary pneumococcal immunogenicity objectives will be achieved if the noninferiority of 20vPnC to 13vPnC for the percentage of participants with the predefined IgG concentration level at 1 month after Dose 3 is established for all 20 serotypes.

For the primary pneumococcal immunogenicity objectives comparing serotype-specific IgG GMCs 1 month after Dose 4, noninferiority will be assessed by the hypothesis test as described in [Section 9.1.2.1.2](#) at an alpha level of 0.05 for each serotype. The primary pneumococcal immunogenicity objectives will be achieved if the noninferiority of the IgG GMCs from the 20vPnC group compared to the 13vPnC group at 1 month after Dose 4 is established for all 20 serotypes.

The overall primary pneumococcal immunogenicity objectives will be achieved if noninferiority of 20vPnC comparing to 13vPnC based on both the percentage of participants with predefined serotype-specific IgG concentration levels at 1 month after Dose 3 and the serotype-specific IgG GMC at 1 month after Dose 4 is demonstrated for all 20 serotypes. Therefore, the overall type I error rate for the primary immunogenicity assessment of the pneumococcal immune response of 20vPnC is well controlled at the 0.05 level.

Concomitant Immunogenicity Evaluation

For the primary concomitant immunogenicity objective comparing immune responses induced by concomitant vaccine antigens at 1 month after Dose 3 from the 20vPnC group to that from the 13vPnC group, noninferiority is assessed by a hypothesis test (Section 9.1.2.2.1) at an alpha level of 0.05 for each concomitant vaccine antigen. The primary concomitant immunogenicity objective will be met if noninferiority is achieved for all concomitant vaccine antigens, diphtheria toxoid, tetanus toxoid, pertussis antigens (PT, FHA, PRN), HBsAg, poliovirus strains, and Hib. Therefore, the type I error rate for the concomitant immunogenicity assessment is well controlled at the 0.05 level.

Note that the noninferiority evaluations of concomitant immunogenicity results comparing the 20vPnC group to the 13vPnC group are meaningful only if the criteria for achieving the pneumococcal immunogenicity objectives are met. Consequently, there is no inflation in the type I error rate for the study, and no type I error adjustments are needed for the concomitant immunogenicity assessments.

